3.2.4 Early Study Drug Discontinuation Assessments

If the subject discontinues study drug prior to the Week 48 Visit, the subject will be asked to return to the clinic within 72 hours of stopping study drugs for the Early Study Drug

Discontinuation Visit. The subject will be asked to continue attending the scheduled study visits through Week 48, unless informed consent has been withdrawn.

At the Early Study Drug Discontinuation Visit, any evaluation showing abnormal results indicating that there is a possible or probable causal relationship with the study drug, will be repeated weekly (or as often as deemed prudent by the Investigator) until the abnormality is resolved, returns to Day 1, or is otherwise explained, or subject has withdrawn consent.

Assessments for the Early Study Drug Discontinuation Visit will follow assessments for Week 48 Visit (see [Section 3.1.3.3](#)) except for FibroScan test. A FibroScan test will be done if this Early Study Drug Discontinuation Visit is also an End-of-Study Visit. Additional safety labs may be done at the discretion of the Investigator.

3.2.5 Criteria for Discontinuation of Study Treatment

Study medication may be discontinued in the following instances:

- Intercurrent illness that would, in the judgment of the Investigator, affect assessments of clinical status to a significant degree. Following resolution of intercurrent illness, the subject may resume study dosing at the discretion of the Investigator.
- Unacceptable toxicity, or toxicity that, in the judgment of the Investigator, compromises the ability to continue study-specific procedures or is considered to not be in the subject's best interest.
- Lack of efficacy.
- Subject requests to discontinue for any reason.
- Subject noncompliance.
- Pregnancy during the study.
- Development of active tuberculosis infection.
- Discontinuation of the study at the request of Gilead, a regulatory agency, or an institutional review board (IRB).

3.2.6 End of Study

The end of study will be the last patient's last observation (or visit).

3.2.7 Post Study Care

After a subject has completed or terminated their participation in the study, long-term care for the subject will remain the responsibility of their primary treating physician.

3.2.8 Virologic Failure

HIV-1 virologic failure is defined as virologic rebound or having HIV-1 RNA ≥ 50 copies/mL at study drug discontinuation, Week 24, or Week 48.

HBV virologic failure is defined as virologic rebound or having HBV DNA ≥ 29 IU/mL at study drug discontinuation, Week 24, or Week 48. Development of tenofovir resistance plus use of an anti-HBV agent (e.g. entecavir) other than the study drug during the treatment period will also be considered a HBV virologic failure.

3.2.9 Management of Virologic Rebound

Subjects who meet the criteria listed below will be considered to have virologic rebound:

HIV-1 Virologic Rebound:

- At any visit, a rebound in HIV-1 RNA ≥ 50 copies/mL, which is subsequently confirmed at the following scheduled or unscheduled visit; OR
- At any visit, a $>1 \log_{10}$ increase in HIV-1 RNA from nadir which is subsequently confirmed at the following scheduled or unscheduled visit.

Following unconfirmed virologic rebound, subjects will be asked to return to the clinic for a scheduled or unscheduled blood draw (2 to 3 weeks after the date of the original test that resulted in HIV-1 RNA virologic rebound) for confirmation of virologic rebound. If virologic rebound is confirmed at the scheduled or unscheduled visit and the HIV-1 RNA is ≥ 500 copies/mL, the blood sample from the confirmation test will be the primary sample used for HIV-1 genotypic and phenotypic testing. Subjects with documented non-adherence within 72 hours of the visit may not be tested for resistance. Resistance testing will be conducted on a case-by-case basis. Any subject may be discontinued at Investigator's discretion.

[figure not shown]
If no resistance is detected, the subject may remain on study drug and a repeat HIV-1 RNA should be repeated (approximately 2 to 3 weeks after date of test with HIV-1 RNA ≥ 50 copies/mL). Investigator should carefully evaluate the benefits and risk of remaining on the study drug for each individual subject and document this assessment in the medical record.

Subject who are noncompliant on an ongoing basis will be considered for discontinuation per the Investigator's discretion.

For subjects who are off study drug but remain on study, it will be the Investigator's discretion to manage virologic rebound.

Figure 6-1 illustrates the algorithm for the management of subjects who meet the criteria for HIV-1 virologic rebound.

Figure 6-1: Virologic Rebound Schema for HIV-1.

HBV Virologic Rebound:

- At any visit, after achieving HBV DNA <29 IU/mL, a rebound in HBV DNA ≥29 IU/mL, which is subsequently confirmed at the following scheduled or unscheduled visit; OR
- At any visit, a >1 log₁₀ increase in HBV DNA from nadir which is subsequently confirmed at the following scheduled or unscheduled visit.

Following unconfirmed virologic rebound, subjects will be asked to return to the clinic for a scheduled or unscheduled blood draw (2 to 3 weeks after the date of the original test that resulted in HBV DNA virologic rebound) for confirmation of virologic rebound. If virologic rebound is confirmed at the scheduled or unscheduled visit and the HBV DNA is ≥500 IU/mL, the blood sample from the confirmation test will be the primary sample used for HBV genotyping and drug resistance assay. Subjects with documented non-adherence within 72 hours of the visit may not be tested for resistance. After a subject's first postbaseline resistance test, additional testing will be conducted on a case-by-case basis. Any subject may be discontinued at Investigator's discretion.

[figure not shown]
If no resistance is detected, the subject may remain on study drug and a repeat HBV DNA should be repeated (approximately 2 to 3 weeks after date of latest test with HBV DNA ≥29

IU/mL). Investigator should carefully evaluate the benefits and risk of remaining on the study drug for each individual subject and document this assessment in the medical record.

Subject who are noncompliant on an ongoing basis will be considered for discontinuation per the Investigator's discretion.

For subjects who are off study drug but remain on study, it will be the Investigator's discretion to manage virologic rebound.

Figure 6-2 illustrates the algorithm for the management of subjects who meet the criteria for HBV virologic rebound.

*Addition of a “3rd” HBV agent in the setting of tenofovir resistance is considered a HBV virologic failure.

4 DISCUSSION OF DESIGN

This is a multicenter, open-label phase 4 study to evaluate the efficacy, safety, and tolerability of treatment with fixed dosed combination B/F/TAF in adults with HIV-1 and HBV coinfection. This study design allows direct assessment of the safety and efficacy of B/F/TAF in this patient population.

Dose: B/F/TAF is FDA-approved as a fixed dose combination one pill once daily taken orally without regards to food. The approved regimen contains 50 mg of bictegravir, 200 mg of emtricitabine, and 25 mg of tenofovir alafenamide. Efficacy of this FDC B/F/TAF for HIV-1 infection has been established based on four double blind, randomized, active control multicenter studies (two treatment naïve and two switch studies) with 1206 subjects receiving B/F/TAF and combined virologic suppression rate of 91.8% at Week 48 by FDA Snapshot analysis. In these studies, less than 1% discontinued B/F/TAF due to adverse events. The selected dosing is therefore most appropriate for use in this study.

Safety Endpoints: The safety assessments used in this trial are standard assessments for Phase 4 studies evaluating the safety of repeated dosing.

Efficacy Endpoints: Assessment of quantitative plasma HIV-1 RNA and HBV DNA is the standard procedure for determining effectiveness of HIV-1 and HBV therapies, respectively. Both primary and secondary efficacy endpoints use both quantitative HIV-1 RNA and HBV DNA levels as main assessment measure. Additional assessments in this trial (e.g. CD4 count, ALT changes, FibroScan test) are also standard measures in trials with HIV-HBV coinfection.

Length of Assessment: The efficacy and safety assessments will be evaluated through end of study. This period spans a total of 48 weeks for all subjects. This duration of assessment is standard in studies involving HIV-HBV coinfection with primary and secondary endpoints marked at Week 24 and Week 48.

Eligibility Criteria: This is a phase 4 switch study for subjects with HIV-HBV coinfection. Eligibility criteria has been designed to include subjects who in real life may or may not be virally suppressed but would benefit from use of B/F/TAF. This will allow a broader applicability of the study results to a much wider HIV-HBV coinfection population. In addition, recent studies have shown that high efficacy was observed among subjects with baseline M184V or M184I who switched to B/F/TAF with 98% of these subjects achieving HIV-1 RNA <50 copies/mL at their last study visit and with no treatment emergent resistance developing ([Andreatta K et al 2019](#)).

5 STUDY POPULATION

The investigators participating in this study have expertise in the diagnosis and management of patients with HIV and HBV. This study will be conducted in the Institute of Human Virology, University of Maryland, Baltimore, MD. Investigators will diagnose subjects with HIV and HBV based on history, physical examination, and laboratory studies.

Participation in this study is voluntary. The nature of the study will be fully explained to each subject during the informed consent process. The subjects will have the opportunity to ask questions. An informed consent document will then be signed by the subject and the person performing the consent discussion, and retained by the investigator according to Good Clinical Practice (GCP). The investigator will retain all documents according to GCP. A copy of the signed informed consent document will be given to the subject.

Eligibility for enrollment will be based on the results of screening utilizing the following inclusion and exclusion criteria.

5.1 Number of Subjects and Subject Selection

This study will enroll approximately 60 subjects who meet the eligibility criteria. We estimate that up to 75 subjects will need to be screened to achieve this enrollment number.

5.2 Inclusion Criteria

Subjects may be included in the study only if they meet all of the following criteria:

1. Age 18 years or older at enrollment.
2. Documented HIV-1 infection and currently on a stable regimen for at least 3 months prior to enrollment.
3. No known history of resistance to TAF, FTC, or BIC except M184V and M184I. Those with M184V or M184I mutations will be allowed to enroll in the study.
4. Documented chronic HBV infection, based on any of the following:
 - a. Positive HBsAg result or nucleic acid test for HBV DNA (including qualitative, quantitative, and genotype testing) or positive HBeAg on two occasions at least 6 months apart (any combination of these tests performed 6 months apart is acceptable); or
 - b. Negative immunoglobulin M (IgM) antibodies to HBV core antigen (anti-HBc IgM) AND a positive results on one of the following tests: HBsAg, HBeAg, or nucleic acid test for HBV DNA (including qualitative, quantitative, and genotype testing) prior to or at screening.

5. No current or prior regimen containing three active anti-HBV agents (drugs active against HBV includes lamivudine [3TC], adefovir [ADV], entecavir [ETV], emtricitabine [FTC], tenofovir disoproxil fumarate [TDF], and tenofovir alafenamide [TAF]).
6. Must have a primary care provider(s) for medical management.
7. Females of childbearing potential must agree to utilize protocol recommended highly effective contraceptive methods or be non-heterosexually active or practice sexual abstinence (as defined in [Appendix F](#)) from screening and throughout the duration of the study. Female subjects who utilize hormonal contraceptive as one of their birth control methods must have used the same method for at least 3 months prior to study drug dosing.
8. Male subjects must be willing to abstain from heterosexual intercourse or use a condom throughout the study period.
9. Stated willingness to comply with all study procedures and availability for the duration of the study.
10. Written informed consent must be obtained before any study procedure is performed.

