3.2.1 Pretreatment Assessments

3.2.1.1 Screening Assessments (Day -90 to Day -3)

The following screening assessments must be done to determine subject eligibility. Written consent will be obtained before conducting any study procedures.

- Screen for inclusion/exclusion (see [Section 5](#)).
- Medical History.
- Complete physical examination, including weight, height, and vital signs (blood pressure, respiratory rate, heart rate, and temperature).
- Collect concomitant medication information.
- 12-lead electrocardiogram (ECG).
- Plasma HIV-1 RNA.
- Plasma HBV DNA.
- Quantitative HBsAg level.
- CD4 cell count.
- HBV profile [HBsAg, HBeAg, anti-HBs, anti-HBe, and anti-HBc both IgM and total].
- HCV serology.
- HDV serology.
- Complete blood count [hematocrit, hematocrit, erythrocyte count (RBC), white blood cell count (WBC), percentage and absolute WBC differential counts, platelet count].
- Comprehensive metabolic panel [glucose, blood urea nitrogen, creatinine, sodium, potassium, chloride, total carbon dioxide, calcium, total protein, albumin, total globulin, total bilirubin, alkaline phosphatase, alanine aminotransferase, aspartate aminotransferase].
- Coagulation tests [activated partial thromboplastin time (PTT), prothrombin time (PT), international normalized ratio (INR)].
- Urinalysis.
- Serum pregnancy test for women of childbearing potential (defined as a woman who is physiologically capable of becoming pregnant).

With the exception of the serum pregnancy test, outside clinical laboratory tests may be used for screening if it was done within 90 days of screening.

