5.3 Exclusion Criteria

Subject meeting any of the following criteria will not be eligible to participate in the study:

1. Females who are pregnant or breastfeeding.
2. Any known allergies to any of the components of B/F/TAF.
3. Treatment with another investigational drug within three months of enrollment.
4. Abnormal hematological and biochemical parameters at screening, including:
 - a. Absolute neutrophil count (ANC) < 750 cells/mm³.
 - b. Platelets < 50,000/mm³.
 - c. Hemoglobin < 8.5 g/dL.
 - d. AST or ALT of > 5 times upper limit of normal (ULN).
 - e. Estimated GFR < 30 mL/min/1.73 m².
 - f. Total bilirubin > 1.5 times ULN.
5. Previous or current history of malignancy, other than cutaneous Kaposi's sarcoma, basal cell carcinoma, or resected, non-invasive cutaneous squamous cell carcinoma.
Note: Those with a history of malignancy who are in remission for two or more years may be included in the study.
6. An opportunistic illness indicative of stage 3 HIV diagnosed within the 30 days prior to screening.
7. Subjects experiencing decompensated cirrhosis (e.g. ascites, encephalopathy, or variceal bleeding).
8. Acute hepatitis in the 30 days prior to study entry.

9. Active tuberculosis infection.
10. Subjects receiving ongoing therapy with any medications contraindicated for co-administration with B/F/TAF FDC, including but not limited to the following medications in the table below:

Drug Class	Prohibited Agents [#]
Antiarrhythmic Agent	Dofetilide
Anticonvulsants	Phenobarbital, Phenytoin, Carbamazepine, Oxcarbamazepine
Antimycobacterials	Rifampin, Rifapentine, Rifabutin
GI Motility Agents	Cisapride
Herbal/Natural Supplements	St. John's Wort, Echinacea
Miscellaneous Agents	Mitotane

[#] Administration of any of the above medications must be discontinued at least 30 days prior to the Day 1 visit and for the duration of the study.

11. Current alcohol or substance use that in the opinion of the investigator may interfere with subject study compliance.
12. Any other clinical conditions that in the opinion of the investigator would make the subject unsuitable for the study or unable to comply with the dosing requirements.

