9.2.2.2 Missing = Failure Method for HBV Efficacy Analyses

Similarly, the analysis window at Week 24 for HBV DNA outcomes is defined as from Study Day 140 to Day 196. For HBV DNA analysis, this study will use the missing = failure method. HBV virologic outcome will be defined as follows:

- **HBV Virologic Success:** this includes subject who have the last available HBV DNA <29 IU/mL in the Week 24 analysis window while on study treatment.
- **HBV Virologic Failure:** this includes subjects who
 - a. Have the last available HBV DNA \geq 29 IU/mL in the Week 24 analysis window while on study treatment, or
 - b. Do not have on-treatment HBV DNA data in the Week 24 analysis window regardless of reason (e.g. discontinued study drug due to AE, death or lack of efficacy; missed Week 24 visit; withdrew consent for any reason).

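### Inclusion criterion 4b can admit a resolved acute hepatitis B infection as chronic HBV, and such a subject then scores as an HBV success at Week 24 regardless of the drug

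*Combined protocol and SAP*

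**What the plan says.** Section 5.2, criterion 4, reads "Documented chronic HBV infection, based on any of the following", so either route is enough by itself. The synopsis has the same wording.

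- **Route 4a** needs positive HBV results "on two occasions at least 6 months apart".
- **Route 4b** needs a negative anti-HBc IgM together with a single positive marker, which may be a "nucleic acid test for HBV DNA (including qualitative, quantitative, and genotype testing) prior to or at screening". The other accepted markers are HBsAg and HBeAg. This route has no six-month element.

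The only exclusion that deals with acute hepatitis (Section 5.3, item 8) is "Acute hepatitis in the 30 days prior to study entry".

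Screening (Section 3.2.1.1) includes HBV DNA, quantitative HBsAg and the "HBV profile [HBsAg, HBeAg, anti-HBs, anti-HBe, and anti-HBc both IgM and total". No criterion requires any HBV marker to be positive at that visit.

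Section 9.2.2.2 defines HBV success as "last available HBV DNA <29 IU/mL in the Week 24 analysis window while on study treatment", with no condition on baseline status. Section 9.1 applies this to everyone who took at least one dose.

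**The concern.** The usual purpose of pairing a positive marker with a negative IgM is to separate chronic from acute infection. That works when both results describe the same infection at the same stage. Criterion 4b does not tie them together, and it lets the marker come from the past. Someone who had acute hepatitis B a year ago and cleared it can have a positive HBsAg on file and a negative IgM at screening. On its wording, 4b is met.

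Such a person has no HBV replication to suppress. Their HBV DNA will be below 29 IU/mL whenever it is measured, so they count as a success that carries no information about B/F/TAF. With no control arm, nothing offsets the upward shift in the HBV rate. The trial's hypothesis concerns adults who are coinfected, so the reported rate would partly describe people outside that population. The per-protocol analysis would not remove them, because they breach no eligibility rule.

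**Working it through.** **Step 1. Does anything else close the gap?**

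| Possible safeguard | Where | Effect |
|---|---|---|
| Six-month persistence | 5.2, 4a | Not part of 4b; 4b suffices without it |
| Acute hepatitis exclusion | 5.3, item 8 | Covers 30 days only |
| Age limit on outside laboratory results: "outside clinical laboratory tests may be used for screening if it was done within 90 days of screening" | 3.2.1.1 | Governs the screening tests, not the historical marker in 4b |
| Per-protocol set | 9.1 | Removes violators of key eligibility criteria; these subjects are not violators |
| Subgroups by HBV DNA, HBeAg status and HBsAg level | 9.2.7 | No cut-points and no stated HBsAg-negative stratum; the main HBV rate is unchanged |

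None of these keeps a cleared infection out of the main HBV analysis.

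**Step 2. The plan's own figure.** Section 9.2 states 84% power for HIV-1 suppression with n = 60, null 0.773 and alternative 0.910. By exact binomial calculation, the smallest r with P(X ≥ r | 0.773) ≤ 0.05 is r = 53. The tail probability is 0.0237 (r = 52 gives 0.0514, just too large). Power is P(X ≥ 53 | 0.910) = 0.831, close to the stated 84%. No HBV quantity enters this calculation, so criterion 4 does not affect it. The plan states no null, target or test for HBV.

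**Step 3. Effect on the HBV rate.** Let f be the share of dosed subjects with cleared infection, p the true success rate in current infection, and q the success rate in cleared subjects.

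Observed rate = (1 − f) × p + f × q, so inflation = f × (q − p). With q = 1 this is f × (1 − p).

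Inputs:
- f is not in the documents. I assume 3, 6 or 12 of 60, that is 5%, 10% or 20%.
- p = 91.7%: joint HIV and HBV suppression at 48 weeks in the coinfection switch study of another TAF-containing regimen (Section 1.1.1).
- p = 64%: HBV suppression on TAF in HBeAg-positive chronic HBV (Section 1.1.1), taken as a low case.

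| p | f = 5% | f = 10% | f = 20% |
|---|---|---|---|
| 91.7% | 0.05 × 0.083 = +0.4 points | 0.10 × 0.083 = +0.8 | 0.20 × 0.083 = +1.7 |
| 64% | 0.05 × 0.36 = +1.8 points | 0.10 × 0.36 = +3.6 | 0.20 × 0.36 = +7.2 |

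**Step 4. Allowing for missing = failure.** If 5% of cleared subjects lack a sample in the window (assumption), q = 0.95. The inflation becomes +0.2, +0.3 and +0.7 points at p = 91.7%, and +1.6, +3.1 and +6.2 at p = 64%.

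**Step 5. Per subject.** Replacing one currently infected subject by a cleared one moves the rate by (1 − p)/60. This is 0.083/60 = 0.14 points at 91.7% and 0.36/60 = 0.6 points at 64%.

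**The case against.** The best defence is that 4b is meant to be read as one documented picture of chronic infection. Its stem says chronic, the IgM test is undated, and the timing phrase could cover both results together. On that reading the gap largely closes. Section 5 adds that experienced investigators make the diagnosis from history, examination and laboratory results, and exclusion 12 gives them discretion. An HBsAg-negative, anti-HBs-positive profile would be seen before Day 1. This shows intent and lowers the likely number of cases. It does not make the rule say so, and since version 4.0 two sites have to apply it.

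Four stronger readings are tempting, and the documents do not support them.

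- *That 4b plainly pairs an old marker with a present-day IgM.* The wording permits this but does not specify it.
- *That cleared subjects cannot be told apart from drug-suppressed carriers.* HBV DNA alone may not separate them, but HBsAg is measured at screening and quantitatively on Day 1, and Section 9.2.7 plans strata by HBsAg level. A carrier who is still HBsAg-positive is distinguishable.
- *That each cleared subject adds 1/60, or 1.7 points.* That would need p = 0; the net effect is (1 − p)/60.
- *That 4a has the same fault.* Two positives six months apart followed by HBsAg loss describe an infection that was once chronic. Whether to enrol such people is largely a choice of population, and Section 4 argues for broad applicability.

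It is also fair to say that many truly chronic subjects may enter already suppressed, since about 87% of the source population is on tenofovir (Section 1.1). That favours a high p and hence a small inflation.

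**Conclusion.** The point holds as a gap in wording that can bias a primary endpoint in one direction. Criterion 4b allows a resolved acute infection to count as chronic HBV, and the endpoint definition then scores it as a success whenever an on-treatment sample falls in the window. The size depends on the cleared share, which the documents do not give. For 3 to 12 of 60 cleared, the inflation is 0.4 to 1.7 points if the true rate is 91.7% and 1.8 to 7.2 points if it is 64%, slightly less once missing data count as failures. HIV-1 sample size and power are untouched, and no HBV decision threshold is stated that could be crossed. A reader might infer that the HBV result would be uninterpretable; at the rate seen in the coinfection switch study the effect is under 2 points even with 12 of 60 cleared. This is a cheap improvement.

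**What to change.** 1. Add to criterion 4b, in Section 5.2 and in the synopsis, that HBsAg is positive or HBV DNA is detectable at screening. HBsAg-positive carriers suppressed on their current regimen still qualify, so the switch design is preserved. A separate rule that both results share a date is not needed, because anti-HBc IgM is on the same screening panel.
2. Add to Section 9.2.2 that the HBV primary endpoint is also reported in the subset that is HBsAg-positive or HBV DNA-detectable at screening. This covers subjects already enrolled and anyone who entered through 4a after losing HBsAg, without excluding the latter from the trial.

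Cost: amendment wording and one extra table from data already scheduled for collection, plus a few more screen failures among people whose past infection has cleared.
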